9.6 Safety and Tolerability Assessments

9.6.1 Adverse events

Where changes in severity are recorded in the Case Report Form (CRF), each separate severity of the AE will be reported in the listings, only the most severe will be used in the summary tables. A pre-existing condition is defined as an AE that starts before the subject has provided written informed consent and is ongoing at consent. A non-treatment emergent AE is defined as an AE which starts after informed consent but prior to dosing. A treatment-emergent AE is defined as an AE which occurs postdose or which is present prior to dosing and becomes more severe postdose.

All AEs will be listed. Treatment-emergent AEs will be summarized by diabetic type, treatment, severity and relationship to the study drug. The frequency (the number of AEs, the number of subjects experiencing an AE and the percentage of subjects experiencing an AE) of treatment-emergent AEs will be summarized by treatment, Medical Dictionary for Regulatory Activities (MedDRA) version 20.1 system organ class and preferred term. The summary and frequency AE tables will be presented for all causalities and those considered related to the study drug. Any serious AEs will be tabulated.

Nasal/respiratory/anosmia AEs will be identified using MedDRA preferred term (see Appendix 1 for the list of preferred terms) and summarized by treatment group. The frequency (the number of AEs, the number of patients experiencing an AE, and the percentage of patients experiencing an AE) of nasal/respiratory/anosmia TEAEs for each preferred term will be summarized by treatment.

The time needed for resolution of nasal/respiratory/anosmia AEs will be calculated based on the start and end date/time reported by the investigator and summarized using descriptive statistics. Events that did not resolve will be excluded from calculation of the time to resolution. This analysis will include all AEs (ie, patients experiencing AEs with the same preferred term at different time points will be counted multiple times).

Kaplan-Meier curve for each treatment will be produced for time to resolution of nasal/respiratory/anosmia AEs. If the event did not resolve during the study, then it will be treated as censored observation at the end of the study.

Clinically significant abnormal findings through electrocardiograms (ECGs), nasal inspection, injection site inspection, and physical examination will be captured as AEs.

9.6.2 Concomitant medication

Concomitant medication will be coded using the World Health Organization (WHO) drug dictionary (Version March 2017). Concomitant medication will be listed. A listing of rescue therapy will also be provided for the ARS.

Final, 01 Feb 2018 Page 19 of 26

9.6.3 Clinical laboratory parameters

All clinical chemistry and hematology data will be summarized by parameter and treatment, and listed. Urinalysis data will be listed. Additionally clinical chemistry, hematology and urinalysis data outside the reference ranges will be listed.

Values for any clinical chemistry, hematology and urinalysis values outside the reference ranges will be flagged on the individual subject data listings.

9.6.4 Vital signs

Vital signs data will be summarized by treatment together with changes from baseline, where baseline is defined as Day 1 predose of each period. Figures of mean vital signs and mean changes from baseline profiles by treatment will be presented by treatment.

Furthermore, values for individual subjects will be listed.

The shift of abnormalities of vital signs from baseline to post treatment will also be summarized by treatment group. For this shift analysis, the high limit is 140 mm Hg for systolic blood pressure, 90 mm Hg for diastolic blood pressure, and 100 bpm for pulse; the low limit is 90 mm Hg for systolic blood pressure, 50 mm Hg for diastolic blood pressure, and 50 bpm for pulse.

All timepoints will be presented on summary tables and figures.

9.6.5 Electrocardiogram (ECG)

Triplicate ECG data will be obtained directly from the 12-lead ECG traces. These data include the PR, QT, QTcB intervals, QRS duration and heart rate, where QTcB is the QT interval corrected using Bazett's formula. In addition, the QT interval corrected using Fridericia's formula (QTcF) will be calculated as follows:

$$QTcF = \frac{QT}{\sqrt[3]{60/HR}}$$

The mean of the triplicate data will be used for subsequent calculations. The ECG data will be summarized by treatment together with changes from baseline, where baseline is defined as Day 1 predose of each period. Figures of mean ECG data and mean changes from baseline will be presented by treatment. The frequency of subjects with a maximum increase from baseline in QTcF interval will be summarized for each treatment according to the following categories: >30 ms and >60 ms. In addition, the frequency of subjects with QTcF postdose values, according to the following categories: >450 ms, >480 ms and >500 ms, will be summarized by treatment.

All timepoints will be presented on summary tables and figures.

A plasma LY900018 concentration-QT analysis will be performed to assess the changes from baseline (Day 1 predose of each period) QTcF interval relative to plasma LY900018. BLQ

Final, 01 Feb 2018 Page 20 of 26

LY900018 concentration data will be imputed to 50% of the LLOQ for the purposes of the analysis. The analysis will be performed by plotting change from baseline QTcF against LY900018 concentrations, including all post dosing timepoints. The plot will be produced separately for each treatment and diabetes type.

A mixed effects analysis model will be performed on the change from baseline QTcF values and will include LY900018 concentration as a covariate and subject as a random effect. The results of the model and associated 90% CI will be fitted on the plot and the p-value for the slope reported.

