9.5.3. Electrocardiograms

For each patient, single and triplicate ECGs should be collected according to the Schedule of Activities (Section 2).

Any clinically significant findings from ECGs that result in a diagnosis and that occur after the patient receives the first dose of the investigational product should be reported to Lilly, or its designee, as an AE via CRF.

Single ECGs will be collected and stored locally at the investigator's site.

Triplicate ECGs will be electronically transmitted to a central ECG laboratory designated by Lilly. The central ECG laboratory will perform a basic quality control check (for example, demographics and study details) then store the ECGs in a database. At a future time, the stored ECG data may be overread at the central ECG laboratory for further evaluation of machine-read measurements or to meet regulatory requirements. Triplicate ECGs collected 30 and 15 minutes prior to the start of insulin-induced hypoglycemia on Day 1 of each period will be used to

establish a baseline. The consecutive triplicate ECGs will be obtained at approximately 1-minute intervals.

When scheduled at the same time point, ECGs must be recorded before collecting any blood samples. Patients must be supine for at least 5 minutes before ECG collection and remain supine but awake during ECG collection. Electrocardiograms may be obtained at additional times, when deemed clinically necessary.

Single ECGs will be interpreted by a qualified physician (the investigator or qualified designee) at the site as soon after the time of ECG collection as possible, and ideally while the patient is still present, to determine whether the patient meets entry criteria at the relevant visit(s) and for immediate patient management, should any clinically relevant findings be identified.

If a clinically significant finding is identified (including, but not limited to, changes in QT/corrected QT interval from baseline) after enrollment, the investigator will determine if the patient can continue in the study. The investigator, or qualified designee, is responsible for determining if any change in patient management is needed, and must document his/her review of the ECG printed at the time of collection. Any new clinically relevant finding should be reported as an AE.

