10.3.2.3. Statistical Evaluation of Safety

Safety parameters that will be assessed include safety laboratory parameters, vital signs, and triplicated ECG parameters. The parameters will be listed and summarized using standard descriptive statistics. Additional analysis will be performed if warranted upon review of the data. The details will be provided in the SAP.

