3. INTRODUCTION

This SAP has been developed after review of the Clinical Study Protocol (final version dated 26 October 2017 and protocol amendment (a) (final version dated 05 December 2017).

This SAP describes the planned analysis of the safety, tolerability and pharmacokinetic (PK) and pharmacodynamic (PD) data from this study. A detailed description of the planned TFLs to be presented in the clinical study report (CSR) is provided in the accompanying TFL shell document.

The intent of this document is to provide guidance for the statistical and PK analyses of data. In general, the analyses are based on information from the protocol, unless they have been modified by agreement between Eli Lilly and Company and Covance Early Clinical (EC) Biometrics. A limited amount of information concerning this study (e.g., objectives, study design) is given to help the reader's interpretation. This SAP must be signed off prior to first subject administration for this study. When the SAP and TFL shells are agreed upon and finalized, they will serve as the template for this study's CSR.

This SAP supersedes the statistical considerations identified in the protocol; where considerations are substantially different, they will be so identified. If additional analyses are required to supplement the planned analyses described in this SAP, they may be performed and will be identified in the CSR. Any substantial deviations from this SAP will be agreed upon between Eli Lilly and Company and Covance EC Biometrics and identified in the CSR. Any minor deviations from the TFLs may not be documented in the CSR.

This SAP is written with consideration of the recommendations outlined in the International Council on Harmonisation (ICH) E9 Guideline entitled Guidance for Industry: Statistical Principles for Clinical Trials¹ and the ICH E3 Guideline entitled Guidance for Industry: Structure and Content of Clinical Study Reports².

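### SAP 9.6.5 measures ECG change from predose, where protocol 9.5.3 sets a pre-insulin baseline, and SAP 11 does not declare it; two SAP time lists also depart from the schedule

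*SAP*

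**What the plan says.** **ECG baseline.** Protocol 9.5.3 says that "Triplicate ECGs collected 30 and 15 minutes prior to the start of insulin-induced hypoglycemia on Day 1 of each period" are to be used to "establish a baseline. The consecutive triplicate ECGs will be obtained at approximately 1-minute intervals". The Schedule of Activities (protocol Section 2) lists these two pre-induction triplicates and the predose triplicate as separate time points, and places predose between the stop of the insulin infusion and study treatment. The infusion stops once bedside PG is below 60 mg/dL.

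SAP 9.6.5 reads: "The ECG data will be summarized by treatment together with changes from baseline, where baseline is defined as Day 1 predose of each period". It repeats the choice for the concentration-QT analysis, which is to "assess the changes from baseline (Day 1 predose of each period) QTcF interval relative to plasma LY900018". On averaging it says "The mean of the triplicate data will be used for subsequent calculations", and on display "All timepoints will be presented on summary tables and figures".

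**Rules on departures.** SAP Section 3 says: "This SAP supersedes the statistical considerations identified in the protocol; where considerations are substantially different, they will be so identified". Protocol 10.3 asks that a change of analysis method too small for an amendment be described, with its justification, in the SAP and/or the clinical study report. SAP Section 11 states that there were no changes.

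**Time lists.** SAP 9.6.10 summarises the Nasal and Non-nasal total score at 15, 30, 60 and 90 minutes. SAP 9.6.11 sends the Edinburgh scale to the same analysis and gives no times of its own. SAP 9.5.3 summarises PG at 15, 30, 45, 60 and 90 minutes.

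**The concern.** The two documents name different ECG samples as baseline: one before any insulin, the other in induced hypoglycemia. The SAP's mean ECG changes, its >30 and >60 ms QTcF-increase categories and its concentration-QTcF model all use the second. Someone who reads those tables with protocol 9.5.3 in hand would take them as change from the pre-insulin state, and SAP 11 gives no warning. Comparing safety and tolerability is a secondary objective, and the SAP is meant to serve as the template for the study report, so an uncorrected mismatch would carry into it.

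The time lists are a smaller matter of the same kind. Followed literally, the SAP produces a 90-minute total-score row with no data, leaves the collected 120-minute total score out of that summary, and asks for a 45-minute PG without naming its source.

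**Working it through.** **1. Plan's own figure reproduced.** The schedule gives PG (PD) samples at pre-induction, -5 minutes and predose, then at 5, 10, 15, 20, 25, 30, 40, 50, 60, 90, 120 and 240 minutes. That is 3 + 12 = 15 per period, and 15 × 2 = 30 per patient. Appendix 5 states 30. The count therefore leaves no room for a 45-minute central-laboratory sample, which would make it 16 × 2 = 32.

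**2. ECG baseline, by algebra.** For one patient in one period, let d = predose QTcF − pre-insulin QTcF.

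- SAP change = post − predose = (post − pre-insulin) − d = protocol change − d, at every postdose time.
- d is constant within the period, so the maximum increase also shifts by −d. An SAP increase above 30 ms is a rise above 30 + d from the protocol baseline; above 60 ms is a rise above 60 + d. Each millisecond of d moves both cut-offs by one millisecond. A positive d makes the SAP categories harder to reach and a negative d makes them easier. The documents contain no QTcF values, so neither size nor sign is known.
- The difference between treatments in mean change shifts by −(mean d before LY900018 − mean d before IMG). Both baselines precede glucagon and sequence is randomized, so this is 0 in expectation.
- The absolute categories (>450, >480, >500 ms) and the means at each time point use no baseline and do not move.

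The protocol's baseline rests on 2 × 3 = 6 tracings per period and the SAP's on 3. The SAP averages within a triplicate; neither document says how the two pre-insulin triplicates would be combined.

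**3. Time lists against the schedule (postdose minutes).**

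| Item | SAP | Scheduled | In SAP, not scheduled | Scheduled, not in SAP |
|---|---|---|---|---|
| Questionnaire total score | 15, 30, 60, 90 | 15, 30, 60, 120 | 90 | 120 |
| Edinburgh scale | as questionnaire | 15, 30, 60, 120 | 90, if the list carries over | 120, if the list carries over |
| PG, central laboratory | 15, 30, 45, 60, 90 | the 12 times in step 1 | 45 | 40 and 50 are the nearest |

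For the questionnaire, 1 of 4 listed times is never collected and 1 of 4 collected times is left out. The SAP does not say which times the total-score mixed model (MMRM) uses. For PG, 1 of 5 listed times has no scheduled central sample.

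**4. Bedside PG near 45 minutes.** Protocol 9.2.3 requires bedside readings for 120 minutes, at most 5 minutes apart when PG is below 90 mg/dL and at most 10 minutes apart otherwise. The nearest reading to 45 minutes is then at most 5/2 = 2.5 or 10/2 = 5 minutes away. At the roughly 3-minute spacing assumed in Appendix 5 it is at most 3/2 = 1.5 minutes away.

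**The case against.** The strongest reply concerns the ECG. Protocol 9.5.3 is a collection section and specifies no change-from-baseline analysis. Protocol 10.3.2.3 names no ECG baseline: it says "The parameters will be listed and summarized using standard descriptive statistics", allows additional analyses and leaves details to the SAP. The SAP states its baseline openly, twice, and has to be signed before first dosing, so the choice is prespecified. Predose is also the protocol's baseline for PK and PD and the SAP's for vital signs, and it separates the effect of glucagon from that of hypoglycemia.

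Most of this stands. Predose is defensible, above all for the concentration-QTcF model, and no analysis that the protocol planned has been displaced. What does not stand is the inference that nothing needed declaring. The pre-insulin triplicates are the only ECG baseline the protocol states. The SAP replaces them, and both SAP Section 3 and protocol 10.3 call for such a change to be identified. The conflict is specific to ECG, because the protocol states no different baseline for vital signs.

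On PG, the reply is largely right. The central-laboratory rule is stated for treatment success, SAP 9.5.3 does not restrict its source, and protocol 9.2.4 itself refers to a bedside value at 45 minutes. A reader might infer that the 45-minute summary cannot be produced. The documents do not support that; the defect is an unnamed source.

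On the questionnaire, a reader might infer that the 120-minute data are lost. They are not: they still enter the per-question tables, the shifts to maximal and last severity, and the listings.

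**Conclusion.** The point holds as a mismatch between protocol and SAP that should be corrected, confined to safety and secondary summaries.

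- **ECG.** The mean changes, the two QTcF-increase categories and the concentration-QTcF response are all measured from a baseline other than the one the protocol states, without declaration. The categories are displaced by d, which is unknown. This rests on the schedule's definition of predose, since the SAP does not define the term.
- **Questionnaires.** The 90-minute total score is an error against the schedule. It reaches the Edinburgh scale if SAP 9.6.11 is read as adopting the same times.
- **PG at 45 minutes.** Minor.

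Two stronger readings are tempting. One is that the predose baseline biases the QTcF comparison between treatments. The expected shift is zero, provided that d does not depend on which treatment is about to be given. The other is that a hypoglycemic baseline hides QT prolongation. That needs a positive d, and the documents give no value or sign. The primary non-inferiority analysis uses none of these outputs.

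**What to change.** 1. **SAP 9.6.5 and 11.** Reconcile with protocol 9.5.3 in one of two ways. Either use the pre-insulin baseline for the change summaries and the >30/>60 ms categories, stating how the 30- and 15-minute triplicates are combined, or keep predose and declare and justify it in SAP 11. If predose is kept only for the concentration-QTcF model, that too should be declared. Showing both baselines is optional.
2. **SAP 9.6.10 and 9.6.11.** Replace 90 with 120 minutes for the total-score summary and the MMRM, and state 15, 30, 60 and 120 minutes for the Edinburgh scale.
3. **SAP 9.5.3.** Replace 45 minutes with scheduled central-laboratory times (40 and/or 50), or state that a bedside value is used at 45.

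The cost is SAP wording and some programming, with no new data collection. If the PG MMRM uses the listed times, putting both 40 and 50 in place of 45 raises the times from 5 to 6 per period. The unstructured matrix then grows from 10 × 10 (10 × 11/2 = 55 parameters) to 12 × 12 (12 × 13/2 = 78), with 66 completers planned. That adds some convergence risk, for which the SAP already has fallback structures. Using only one of the two times keeps 55.

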Injection-Site Assessment Nasal Inspection			Pre-hypoglycemia induction, 90 min Pre-hypoglycemia			Pre-hypoglycemia induction, 90 min Pre-hypoglycemia			Injection-site assessment for IMG only. Nasal inspection both for
Vital Signs	X		induction, 90 min Pre-hypoglycemia			induction, 90 min Pre-hypoglycemia	X		IMG and LY900018. Time points may be
(Supine Blood Pressure, Pulse Rate, and Body Temperature)			induction, Predose, 15, 30, 60, 120, 240 min			induction, Predose, 15, 30, 60, 120, 240 min			added for each period if warranted and agreed upon between Lilly and the investigator. Predose time point will be between insulin infusion stop and study treatment.
Single 12-lead ECG (Local)	X						X		
Triplicate 12-lead ECG (Central)			Pre-hypoglycemia induction (30 and 15 min prior to insulin infusion), Predose, 15, 30, 60, 120, 240 min			Pre-hypoglycemia induction (30 and 15 min prior to insulin infusion), Predose, 15, 30, 60, 120, 240 min			Time points may be added for Period 1 and Period 2 if warranted and agreed upon between Lilly and the investigator. Predose time point will be between insulin infusion stop and study treatment.
Laboratory Tests									
Clinical Serology Tests	X								See Appendix 2, Clinical Laboratory Tests, for details.

	Screening		Period 1	Wash out		Period 2	Follow-up/ED	Additional Follow-up for TE ADA ^a	Comments
Procedure	Days -28 to -2	Day -1	Day 1	3 to 14 days	Day -1	Day 1	Within 28±2 days after last study treatment		
Clinical Lab Tests (Hematology, Clinical Chemistry, and Urinalysis)	X		Pre-hypoglycemia induction			Pre-hypoglycemia induction	X		See Appendix 2, Clinical Laboratory Tests, for details. Patients do not need to fast for samples at screening or follow-up. At Periods 1 and 2, samples should be collected from patients who have fasted at least 8 hours before any study procedures.
HbA1c	X		Pre-hypoglycemia induction						See Appendix 2, Clinical Laboratory Tests, for details.
Pregnancy Test (Female patients of childbearing potential only)	X	X			X		X		Serum pregnancy test will be performed at screening. Urine pregnancy test will be performed at every admission period and follow-up visit if applicable.
FSH (Female patients only)	X								When needed to confirm postmenopausal status.
Ethanol Testing	X								Additional tests can be done at the discretion of the investigator.

	Screening		Period 1	Wash out		Period 2	Follow-up/ED	Additional Follow-up for TE ADA ^a	Comments

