Procedure	Days -28 to -2	Day -1	Day 1	3 to 14 days	Day -1	Day 1	Within 28±2 days after last study treatment		
Urine Drug Screen	X								Additional tests can be done at the discretion of the investigator.
PK (Glucagon)			Pre-hypoglycemia induction, Predose, 5, 10, 15, 20, 25, 30, 40, 50, 60, 90, 120, 240 min			Pre-hypoglycemia induction, Predose, 5, 10, 15, 20, 25, 30, 40, 50, 60, 90, 120, 240 min	X	X	Sampling times are relative to the time of study treatment administration (0 min). Predose time point will be between insulin infusion stop and study treatment.
Plasma Glucose for PD			Pre-hypoglycemia induction, -5, Predose, 5, 10, 15, 20, 25, 30, 40, 50, 60, 90, 120, 240 min			Pre-hypoglycemia induction, -5, Predose, 5, 10, 15, 20, 25, 30, 40, 50, 60, 90, 120, 240 min			-5 mins = stop insulin infusion. Sampling times are relative to the time of study treatment administration (0 min). Predose time point will be between insulin infusion stop and study treatment.
Genetic Sample (Stored)		X							Single sample for pharmacogenetic analysis taken prior to/on Period 1 Day -1.

	Screening		Period 1	Wash out		Period 2	Follow-up/ED	Additional Follow-up for TE ADA ^a	Comments
Procedure	Days -28 to -2	Day -1	Day 1	3 to 14 days	Day -1	Day 1	Within 28±2 days after last study treatment		
Anti-glucagon Antibodies			Pre-hypoglycemia induction				X	X	In the event of drug hypersensitivity reactions (immediate or non-immediate), samples will be collected as close to event onset as possible, at event resolution, and 30 days following the event. Patients with TE ADA at follow-up/ED will undergo additional follow-up. Refer to Section 9.7.1 for details.
Health Outcome Instruments									
Clarke Hypoglycemia Awareness Survey		X							
Nasal and Non-nasal Score Questionnaire			Pre-hypoglycemia induction, 15, 30, 60, 120 min			Pre-hypoglycemia induction, 15, 30, 60, 120 min			Sampling times are relative to the time of study treatment administration (0 min). Questionnaire will be collected in both LY900018 and IMG treatment groups in both periods.

	Screening		Period 1	Wash out		Period 2	Follow-up/ED	Additional Follow-up for TE ADA ^a	Comments
Procedure	Days -28 to -2	Day -1	Day 1	3 to 14 days	Day -1	Day 1	Within 28±2 days after last study treatment		

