5.4. Scientific Rationale for Study Design

This study design involves an open-label assessment of 3 mg LY900018 compared to 1 mg of the marketed IMG (GlucaGen). The study will be open label because the different administration routes (ie, intranasal and IM) cannot be blinded. The use of a crossover design allows each patient to serve as his or her own control, thereby reducing variability. The washout period of 3 to 14 days is considered sufficient based on the short half-life of LY900018 (t_{1/2} = approximately 25 minutes). Since the critical role of glucagon in the treatment of severe hypoglycemia is to raise the PG level sufficiently to restore cognition to the point where oral carbohydrate can be ingested, treatment success is defined either as an increase in PG returning to normal level of ≥70 mg/dL or an increase of ≥20 mg/dL from the PG nadir within 30 minutes after receiving glucagon, without the patient receiving additional actions to increase glucose. It is believed that an expected PG nadir of approximately 50 mg/dL (approximately 5 minutes after stop of insulin infusion at 60 mg/dL) is low enough to generate clinical symptoms in most participants and is high enough to avoid impairment of consciousness. The primary analysis includes both patients with T1DM and T2DM since it is expected that the proportion of treatment success is similar between patients with T1DM and T2DM.

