7. SAMPLE SIZE JUSTIFICATION

Seventy five patients may be enrolled in order to have at least 66 patients (at least 30 patients with T1DM and T2DM, respectively) complete the study. For purposes of this study, a completer is defined as a patient who completes both periods with evaluable primary outcome. If patients discontinue from the study before completion of both periods with evaluable primary outcome for any reason, the patient may be replaced to ensure 66 patients complete the study. The replacement patients will be assigned the same treatment sequence as the patients to be replaced and will complete that treatment sequence in its entirety. Replacement should not occur beyond 75 patients enrolled, if it is expected to have at least 66 patients complete the study.

Assuming a non-inferiority margin (NIM) of 10%, a 98% treatment success rate for both treatment groups, and a within-patient correlation of zero, 66 completers will provide at least 90% power to show non-inferiority between LY900018 and IMG in treatment success from insulin-induced hypoglycemia with one-sided alpha level of 0.025 based on the Chi-square test.

The proposed NIM of 10% has been chosen based on the previously completed Phase 3 study (Rickels et al. 2016)³.

Final, 01 Feb 2018 Page 8 of 26

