9.4.2 Pharmacokinetic Statistical Methodology

The PK parameters will be statistically analysed, listed and summarized by diabetic type and overall.

Log-transformed PK parameters (such as C_{max} and AUC) will be evaluated in a linear mixed-effects model with fixed effects for treatment, period, and sequence, and a random effect for patient. The treatment differences will be back-transformed to present the ratios of geometric means and the corresponding 90% confidence intervals (CIs).

Example SAS code:

```
proc mixed data=test covtest alpha=0.1;
  by parameter;
  class treatment patient period sequence;
  model log_pk = treatment period sequence / ddfm=kr alpha=0.1;
  random patient;
  lsmeans treatment / pdiff cl alpha=0.1;
  ods output lsmeans=lsmeans;
  ods output diffs=diffs;
  ods output covparms=cov;
run;
```

The t_{max} will be analyzed using the Wilcoxon signed-rank test. Estimates of the median difference based on the observed medians, 90% CIs, and p-values from the Wilcoxon test will be calculated.

Exploratory analyses may be performed for other PK parameters as deemed appropriate.

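### The concentration-QTcF model names only a subject random effect; without a random slope, its slope p-value is too small whenever slopes differ between patients

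*SAP*

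**What the plan says.** SAP 9.6.5 describes a concentration-QT analysis made by "plotting change from baseline QTcF against LY900018 concentrations, including all post dosing timepoints", with a separate plot for each treatment and diabetes type. A mixed model for the change in QTcF "will include LY900018 concentration as a covariate and subject as a random effect". On reporting: "The results of the model and associated 90% CI will be fitted on the plot and the p-value for the slope reported".

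The section names no random slope, within-patient covariance structure, robust variance or degrees-of-freedom method. It does not say in words that the random effect is an intercept only. That is the ordinary reading, and it matches the SAP's own PK code in 9.4.2, where the patient effect is coded "random patient".

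The Schedule of Activities (Protocol Section 2) takes triplicate ECGs at "Predose, 15, 30, 60, 120, 240 min" and PK samples at "Predose, 5, 10, 15, 20, 25, 30, 40, 50, 60, 90, 120, 240 min". Each patient therefore gives five matched post-dose pairs per period. SAP 9.6.14 says that no inferential safety analysis is planned, and 9.6.5 attaches no significance level or decision threshold to the slope.

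**The concern.** The question of interest is whether QTcF rises with concentration on average across patients. A model with one common slope treats a patient's five ECGs as independent once the intercept is removed. If patients have different slopes, that variation goes into the residual and is averaged over all ECGs. It should be averaged over patients, because a patient's slope is shared by all five of that patient's ECGs. The slope standard error is then too small.

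This is the only model-based cardiac inference in the trial; the other ECG outputs are summaries and category counts. A p-value that is too small can suggest a QT relation that is not there. Variation in slope is plausible: the sample mixes type 1 and type 2 diabetes with different age and BMI limits, and Protocol 3.3 describes chronotropic effects of glucagon, while QTcF is computed from heart rate.

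**Working it through.** The documents state no error rate, power or variance for this model, so there is no planned figure to reproduce.

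**Inputs from the documents.** ECG times 15, 30, 60, 120 and 240 min, so k = 5; half-life "approximately 25 minutes" (Protocol 5.4); "Seventy five patients may be enrolled in order to have at least 66 patients" (SAP 7), at least 30 per diabetes type.

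**Assumptions, not in the documents.** Absorption rate 0.1/min; residual SD σ = 5 to 8 ms; intercept SD about 6 ms; between-patient exposure CV 30% or 60% (lognormal); between-patient slope SD τ = 1 to 5 ms, expressed as the QTcF change at the typical patient's peak concentration; mean slope zero.

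**Step 1: spread of concentration within a patient.** With elimination rate ln 2/25 = 0.0277/min, the typical profile relative to its peak at the five times is 0.988, 0.873, 0.423, 0.081, 0.003 (mean 0.474). The sum of squared deviations is S0 = 0.265 + 0.159 + 0.003 + 0.154 + 0.222, about 0.802. A patient with relative exposure A has S = A²·S0.

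**Step 2: true against reported variance of the slope** (within-patient approximation):

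- true: (σ²ΣS + τ²ΣS²)/(ΣS)²
- reported: [σ² + τ²·mean(S)/(k − 1)]/ΣS

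For lognormal exposure with median 1, E[A⁴]/E[A²] = (1+CV²)⁶ and E[A²] = (1+CV²)². Hence

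R² = true/reported = [σ² + τ²·S0·(1+CV²)⁶] / [σ² + τ²·S0·(1+CV²)²/4].

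The number of patients cancels, which is why a larger sample is no cure. Rejection at nominal 5% is about 2Φ(−1.96/R).

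**Step 3: example, σ = 5, τ = 3.**

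- CV 60%: (1.36)⁶ = 6.33 and (1.36)² = 1.85. R² = (25 + 9×0.802×6.33)/(25 + 9×0.802×1.85/4) = 70.7/28.3 = 2.49, so R = 1.58 and rejection is 2Φ(−1.24) = 21%.
- CV 30%: (1.09)⁶ = 1.68 and (1.09)² = 1.19. R² = 37.1/27.1 = 1.37, so R = 1.17 and rejection is 2Φ(−1.68) = 9%.

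**Step 4: the grid, formula beside simulation.** The simulations fit the random-intercept model by REML, 66 patients, at least 1,000 runs per cell. Ranges run over σ = 8 to 5 ms.

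| Slope SD (ms) | CV 30%, formula | CV 30%, simulated | CV 60%, formula | CV 60%, simulated |
|---|---|---|---|---|
| 0 | 5% | about 5% | 5% | about 5% |
| 1 | 5–6% | 5–6% | 6–7% | 6–8% |
| 2 | 6–7% | 6–8% | 8–13% | 9–13% |
| 3 | 7–9% | 7–9% | 12–21% | 14–20% |
| 5 | 10–15% | 10–14% | 22–35% | 23–34% |

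Sample size, checked at σ = 6, τ = 4: 11.5% with 33 patients and 11.4% with 70 (CV 30%); 25.0% and 27.1% (CV 60%).

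**Step 5: the two possible 90% intervals.** A 90% CI for the slope covers 80–84%, 72–80% and 57–69% at τ = 2, 3 and 5 ms (CV 60%, simulated). At CV 30% the formula gives 87–89%, 84–87% and 77–84%. The band around the fitted line behaves better. In simulation over both CVs it covers 88–91% at half the typical peak for every τ from 0 to 5 ms. At the peak it covers 88–90% for τ = 1–2 ms, 83–87% for 3 ms and 79–85% for 5 ms.

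**Step 6: does a random slope repair it?** With uncorrelated random intercept and slope, t on n − 1 degrees of freedom, σ = 6, τ = 0 to 6 ms, 33 or 66 patients and 400 runs per cell, rejection is 3.3–6.8% at nominal 5% and 7.7–12.2% at nominal 10%. For τ = 2 to 6 ms the random-intercept standard error is 0.61 to 0.92 of the random-slope one. Subject-clustered sandwich errors gave 4–10% at nominal 5% over τ = 0 to 12 ms.

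**The case against.** The strongest reply has four parts.

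1. **Size.** A reader might infer that the test is several times too liberal as a matter of course. The documents do not support a fixed multiplier: slope SD, residual SD and exposure CV are all absent, and CV alone moves the answer a great deal. At CV 30% a doubling needs a slope SD near 5 ms when σ = 5, which would mean roughly one patient in six lengthening and one in six shortening QTcF by more than 5 ms at the peak. This stands; only a range can be given.
2. **Interval.** A reader might infer that the 90% CI is badly narrow and that a real QT effect is therefore easily ruled out. The SAP text most naturally describes a band around the fitted QTcF line, and Step 5 shows that band holding up well except near the peak with large slope variation. This stands as well; the complaint is mainly about the p-value.
3. **Use.** No decision depends on the slope, SAP 9.6.14 disclaims inference on safety, and the QTcF category counts do not use this model. This limits the severity, but 9.6.5 still commits to a p-value that readers will interpret.
4. **Reading.** The text does not literally exclude a random slope. True, but a programmer following it and the PK code would fit an intercept, so the wording needs settling either way.

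**Conclusion.** The point holds as a low-severity improvement. On its ordinary reading the model assumes one slope for all patients. If slopes differ, the slope p-value is anti-conservative at any sample size. Under the stated assumptions the false-positive rate at nominal 5% runs from about 5% to 14% at exposure CV 30% and from about 6% to 34% at CV 60%, for slope SDs of 1 to 5 ms, and stays at 5% if slopes are equal. A 90% CI for the slope would be too narrow in the same settings; the plotted band much less so. The direction is certain given differing slopes. The size is not, since every variance used is assumed. The primary endpoint is unaffected.

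**What to change.** In SAP 9.6.5, specify a random intercept and a random slope on concentration for each subject, with unstructured covariance and Kenward-Roger degrees of freedom. Take the slope p-value and the plotted 90% CI from that fit. State the fallback order if it does not converge: uncorrelated intercept and slope, then the random-intercept fit with sandwich standard errors clustered on subject.

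This is one sentence and one changed RANDOM statement, with no new data. It is in keeping with the SAP's own practice: GEE and an aggregated robust variance in 9.3.2, and Kenward-Roger with an ordered convergence fallback in 9.5.3.

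The costs are a somewhat wider interval, possible non-convergence (covered by the fallback) and perhaps a slightly conservative test if slopes do not differ. The unstructured, Kenward-Roger version was not itself simulated; the check above used uncorrelated effects. The sandwich fallback is imperfect (up to about 10% at nominal 5%), so it belongs last.
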